I will provide all study personnel under my supervision with copies of the protocol and access to all information provided by the sponsor or its representative. I will discuss this material with them to ensure that they are fully informed about the efficacy and safety parameters and the conduct of the study in general. I am aware that, before beginning this study, the institutional review board responsible for such matters must approve this protocol in the clinical facility where it will be conducted.

I agree to provide all subjects with informed consent, as required by government regulations and the ICH guidelines. I further agree to report to the sponsor or its representative any adverse events in accordance with the terms of this protocol and the U.S. Code of Federal Regulations, Title 21, part 312.

Principal Investigator name (print)

Signature

Date

STUDY PRINCIPAL INVESTIGATOR SIGNATURE

Study Title: Adenosine Contrast CorrELations in Evaluating RevAscularizaTION (The ACCELERATION Study)

Version: 5.0

Date of Issue: March 23rd, 2022

I have read and approve this protocol and agree on its content.

[name], FACC, FSCAI

Date

Sponsor:
Duke Clinical Research Institute

PROTOCOL VERSION AND AMENDMENT TRACKING

Version Number/Amendment	Approval Date
Protocol: Version 1.0	February 6, 2018
Protocol: Version 2.0	June 5, 2018
Protocol: Version 3.0	July 25, 2018
Protocol: Version 4.0	August 18, 2020
Protocol: Version 5.0	

PROTOCOL SYNOPSIS

Protocol Title	Adenosine Contrast CorrELations in Evaluating ReVascularizaTION (The ACCELERATION Study)
Main Criteria for Inclusion	Patients > 18 years old. All subjects who are clinically stable and undergoing non-emergent cardiac catheterization for appropriate indications. Diagnostic angiogram reveals at least one moderate (40-70%) stenosis by angiographic assessment.
Study Objectives	To evaluate the NAVVUS fractional flow reserve (FFR) device, as follows: 
 • Determine the accuracy and correlation of contrast FFR (cFFR) using the ACIST CVi automated contrast injector to the current gold-standard adenosine FFR (aFFR) • Evaluate the association of post-percutaneous coronary intervention (PCI) FFR to long-term clinical outcomes (death, myocardial infarction [MI], target vessel revascularization [TVR]) with up to 1-year follow-up
Study Design	The ACCELERATION study is an investigator-initiated, multicenter, prospective, single-arm trial evaluating the method of delivery of contrast for FFR with use of the NAVVUS RXi microcatheter FFR system and the CVi automated contrast injector in patients with intermediate lesion coronary artery disease. Up to 200 subjects undergoing non-emergent PCI from approximately 5 centers will be enrolled. After NAVVUS FFR-guided PCI (with contrast and aFFR measurements), subjects will be contacted for follow-up at 30 days and 1 year by the enrolling site. Primary endpoint results will be reported after all subjects have completed the 30-day clinical follow-up.
Treatment Regimen	Patients with intermediate lesions meeting the clinical and angiographic inclusion/exclusion criteria will be enrolled. NAVVUS FFR will then be performed with contrast and aFFR. Contrast for cFFR will be injected via the ACIST CVi contrast injector with standardized settings, and adenosine for aFFR will be delivered systemically via intravenous infusion. If PCI is performed, a final post-PCI contrast and aFFR will be obtained.
Duration of Subject Study Participation	Sites will see patients for their standard-of-care follow-up visit approximately 30 days after their procedure. Patients will be contacted at 1 year to collect data for the secondary endpoint analysis.
Number of Patients	Up to 200 subjects
Number of Sites	Approximately 5 centers are planned in the US.

Objective/Endpoints for Evaluating the ACIST NAVVUS FFR microcatheter and ACIST contrast power injector.	
Primary Objective/Endpoint:
 
(1) Perform a methods comparison between cFFR and the reference standard aFFR, where cFFR is performed using an automated injector with a standardized volume and rate of delivery of contrast with known osmolality.
 
Secondary Objective/Endpoint:
 
(1) Evaluate the association between final post-PCI FFR and long-term clinical outcomes. The long-term clinical outcomes will include TVR and composite major adverse cardiac events (death, MI, and TVR) at index hospitalization (prior to discharge), 30 days and 1 year.

Statistical Analysis Sample Size/ Power Considerations	Up to 200 patients with intermediate lesions (see statistical analysis plan in protocol for details)

TABLE OF CONTENTS

Statement of Compliance	2
Site Principal Investigator Statement	3
Study Principal Investigator Signature.....	4
Protocol Version and Amendment Tracking	5

Figure 2: Sample Size by AUC by various ratio of negative to positive	32
---	----

ABBREVIATIONS

ACT	activated clotting time
ADE	adverse device effect
AE	adverse event
aFFR	adenosine fractional flow reserves
AUC	area under the curve
CAD	coronary artery disease
cFFR	contrast fractional flow reserve
DCRI	Duke Clinical Research Institute
dPR	diastolic pressure ratio
eCRF	electronic case report form
EDC	electronic data capture
FDA	Food and Drug Administration (US)
FFR	fractional flow reserve
HR	hazard ratio
ICF	informed consent form
iFR	instantaneous wave free ratio
IFU	instructions for use
IRB	institutional review board
ITT	intent to treat
IV	Intravenous
LAR	legally authorized representative
MACE	major adverse cardiac events
MI	myocardial infarction
NCDR	National Cardiovascular Data Registry
OMT	optimal medical therapy
Pd/Pa	intracoronary distal pressure/aortic pressure
PCI	percutaneous coronary intervention

ROC	receiver operating characteristics
RR	relative risk
SAE	serious adverse event
SD	standard deviation
TVR	target vessel revascularization
UADE	unanticipated adverse device effect

1. INTRODUCTION AND BACKGROUND

Fractional flow reserve (FFR) has emerged as an effective invasive means of assessing the physiologic significance of an epicardial coronary stenosis. The test complements the visual assessment of a stenotic lesion based solely on anatomic features during angiography. The addition of FFR to the diagnostic armamentarium of interventional cardiologists has significantly impacted best practice recommendations for how and when to treat coronary lesions with percutaneous coronary intervention (PCI), selecting only ischemic lesions supplying viable myocardium. This disruptive technology received widespread utilization after multiple, large randomized controlled trials demonstrated superior patient outcomes with FFR-guided PCI compared with standard angiography-guided PCI.

The initial FAME trial was a randomized, prospective trial of 1,005 patients with stable, multivessel coronary artery disease (CAD) of >50% angiographic stenosis who were assigned to an angiography vs FFR-guided strategy in selecting lesions amenable to PCI. The primary endpoint of major adverse cardiac events (MACE) (including death, myocardial infarction (MI), repeat revascularization) occurred in 91 patients (18.3%) in the angiography group and in 67 patients (13.2%) in the FFR-guided group (relative risk [RR] 0.72, 95% CI 0.54-0.96, $p=0.02$). The utilization of FFR significantly reduced the total number of stents placed (2.7 vs 1.9), total length of stents (51.9 mm vs 37.9 mm), cost of materials (\$6,007 vs \$5,332), and hospital length of stay (3.7 days vs 3.4 days) (1).

FAME 2 built on the evidence from FAME and included an optimal medical therapy (OMT) arm. In this trial, 888 multivessel CAD patients with at least 1 FFR positive lesion were randomized to FFR-guided PCI with drug-eluting stents plus OMT or OMT alone. The primary endpoint was a composite of death, MI, hospitalization, or urgent revascularization. The study was prematurely halted after interim analysis revealed a statistically significant decrease in unplanned hospitalization leading to urgent revascularization in the FFR-PCI arm (1.6% vs 11.1%, hazard ratio [HR] 0.13, 95% CI 0.06-0.30, $p<0.001$). This drove a significant reduction in the primary endpoint for FFR-guided PCI plus OMT as compared to OMT alone (4.3% vs 12.7%, HR 0.32, 95% CI 0.19-0.53, $p<.001$) (2).

Based on FAME and other supporting data, FFR was incorporated into the 2011 American College of Cardiology/American Heart Association/Society for Cardiac Angiography and Interventions guidelines for PCI. The adjunctive device received a class IIa indication for assessment of angiographic intermediate coronary lesions to guide revascularization decisions in patients with stable ischemic heart disease (3). Fractional flow reserve is also an integral component of the multi-society-supported Appropriate Use Criteria for coronary revascularization (4-6).

As FFR utilization increases in clinical practice, various methods for inducing hyperemia have emerged. These methods are primarily designed to circumvent inherent risks associated with the use of adenosine, as well as decrease time and improve workflow in the catheterization laboratory, without compromising accuracy. Some challenges with traditional systemic intravenous (IV) adenosine administration for FFR measurement are: 1) heart block; 2) other undesirable patient side effects, including chest

pain, bronchospasm, and shortness of breath; 3) relative contraindications in patients with obstructive lung disease or recent caffeine use; 4) added time to prepare and infuse adenosine; and 5) associated costs. Intracoronary adenosine push is still associated with similar risks and limits the operator from assessing diffuse or tandem lesions given the shorter time frame of peak hyperemia. Alternative strategies include a measurement of resting physiologic gradients (distal pressure/aortic pressure [Pd/Pa], diastolic pressure ratio [dPR], and instantaneous wave free ratio (iFR). iFR assesses the gradient during a short period in diastole when resistance across the coronary vasculature is stable (the “wave free” period). During this time, coronary flow and pressure are proportional and the trans-lesion gradient approximates flow and lesion severity. iFR correlation to traditional hyperemia-induced FFR is moderate, yet strengthened by data that support conversion to FFR only in a pre-defined “yellow zone” (i.e., 0.86 to 0.93). Lesions with values in the “green zone” and “red zone” can be safely deferred or intervened, respectively, without the need for adenosine fractional flow reserves (aFFR). iFR with set protocols based on these zones received US Food and Drug Administration (FDA) clearance in 2014. Measurement of dPR is not proprietary and can be acquired during real-time resting gradient assessment or via post-procedure analysis of the resting gradient waveforms. dPR has been shown to be numerically equivalent to iFR regardless of the time period acquired within the diastolic period (7).

An emerging adenosine-free alternative is contrast-induced FFR (cFFR). Conventional non-ionic radiographic contrast medium has been shown to induce submaximal reactive hyperemia and Pd/Pa ratio measured post-contrast injection has been reported to approximate traditional FFR values (8). A prospective study with 80 patients and 104 intermediate lesions found a strong correlation between cFFR and aFFR ($r=0.94$, $p<0.001$). Receiver operating characteristics (ROC) curve analysis showed an excellent accuracy of a cFFR cut-off of ≤ 0.83 in predicting an FFR value ≤ 0.80 (area under the curve [AUC] 0.97, 95% CI 0.91-0.99, specificity 96.1, sensitivity 85.7). No cFFR value ≥ 0.88 corresponded to an FFR value ≤ 0.80 . These data suggest that cFFR ≤ 0.83 is significant, ≥ 0.88 is non-significant, and borderline values in between should be further assessed with aFFR for induction of maximal hyperemia (8).

A recent international study of 763 patients sought to compare the diagnostic performance of aFFR with the spectrum of alternative FFR modalities, including Pd/Pa, iFR, and cFFR (9). Pd/Pa and iFR had equivalent performances against FFR ≤ 0.80 with ~80% accuracy. cFFR improved this accuracy to 86%. A significant limitation of this study was the lack of a standardized protocol for the type, volume, and rate of intracoronary contrast injection. These considerations were left to the operator’s discretion, including the use of either manual (manifold) injection or an automated injector system, and the choice of contrast agents with different osmolalities. Standardizing these contrast and injection parameters could further improve the diagnostic accuracy of cFFR (9). This hypothesis forms the basis for the current proposed study.

While pre-PCI FFR is now an established modality, there remains limited data on whether immediate, post-PCI FFR might have an important long-term clinical impact. A recent systematic review and meta-analysis included 59 studies evaluating the relationship between post-PCI FFR and clinical outcomes up to 30 months. In general, higher post-PCI FFR values were associated with reduced rates of repeat interventions

and MACE. A post-PCI FFR ≥ 0.90 was associated with a 57% RR reduction of repeat PCI and a 30% RR reduction of MACE (10). In a multicenter registry of 750 patients, post-PCI FFR was the most significant independent predictor of clinical events (11). Death, MI, and target vessel revascularization (TVR) at 6 months were stratified by categories of immediate post-PCI FFR values and found to be 4.9% (post-FFR > 0.95), 6.2% (post-FFR 0.90-0.95), and 20.3% (post-FFR < 0.90). In the minority of patients with a post-FFR < 0.80 , the event rate was exceedingly high at 29.5%. The proposed study will add to the growing body of literature supporting use of post-PCI in routine clinical practice, particularly as the field moves towards adenosine-free FFR acquisition techniques.

2. OBJECTIVES

The ACCELERATION study will support a safer approach to FFR for patients by potentially reducing toxic drug exposure (adenosine) if cFFR with standardized injection settings is observed to have a strong correlation to traditional FFR. In addition, ACCELERATION will utilize the novel NAVVUS RXi microcatheter FFR technology in intermediate lesions, which will promote optimal vessel access with a workhorse wire of the operator's choosing during pre- and post-PCI FFR measurements. The 2 main objectives of the study are:

1. Perform a methods comparison between cFFR and the reference standard aFFR, where cFFR is performed using an automated injector with a standardized volume and rate of delivery of contrast with known osmolality.
2. Evaluate the association between final post-PCI FFR and long-term clinical outcomes. The long-term clinical outcomes will include TVR and composite MACE (death, MI, and TVR) at 30 days and 1 year.

[figure not shown]
3. STUDY DESIGN

3.1 Overview of Study

The ACCELERATION study is an investigator-initiated, multicenter, prospective, single-arm trial evaluating optimal acquisition techniques of FFR using the NAVVUS RXi microcatheter FFR system in patients with intermediate lesion CAD. The study will determine the accuracy and correlation of cFFR (using the ACIST CVi automated contrast injector) to the current gold-standard aFFR, and evaluate the association of post-PCI FFR to long-term clinical outcomes including TVR and MACE with 1-year follow-up.

Figure 1 depicts the study flow diagram with clinical and angiographic screening criteria. The enrollment cap is controlled at 200 subjects between 5 centers.

Figure 1. Study Design and Treatment Schema

aFFR, adenosine fractional flow reserve; CHF, congestive heart failure; COPD, chronic obstructive pulmonary disease; CVi, ACIST automated contrast injector; dPR, diastolic pressure ratio; FFR, fractional flow reserve; NSTEMI, non-ST-elevation myocardial infarction; PCI, percutaneous coronary intervention; SA, stable angina; UA, unstable angina

3.2 Procedural Steps

3.2.1 Angiographic Confirmation Eligibility

Patients will be enrolled in the study following angiographic confirmation of a target vessel with an intermediate coronary lesion(s) that meet the inclusion and exclusion criteria. Serial stenosis or diffuse disease can be included if the operator would normally assess these lesions with FFR and plan for PCI if positive. 1 vessel per patient can be enrolled in the study.

3.2.2 Procedural Planning

Operators should use FFR per their usual practice and follow standard of care per clinical guidelines and appropriate use criteria. The protocol calls for a recording of resting Pd/Pa, dPR (in real-time or post-procedure waveform analysis), contrast FFR, and adenosine FFR every time a physiologic assessment is made. The protocol also requires the same measurements immediately post-PCI. Below are specific procedural details to ensure uniformity across sites. Any deviations should be recorded.

1. Access site, guide catheter (minimum 6F), 0.014" coronary workhorse wire, and antiplatelet/anticoagulant strategy will be at the discretion of the operator.
2. Systemic anticoagulation confirmation will be achieved by activated clotting time (ACT) measurement prior to coronary wire exiting the guide catheter.
3. After wiring the lesion, administer 1-200 micrograms of intracoronary nitroglycerin and chase with saline to clear the guide catheter. Await return of baseline blood pressure prior to hemodynamic measurement
4. Resting Pd/Pa, dPR, contrast FFR, and adenosine FFR will be obtained for each physiologic assessment based on the following procedural steps:
 - a. Equalization
 - i. NAVVUS RXi FFR microcatheter will be advanced until guide exit and equalized.
 - ii. Equalization step will be performed each time the NAVVUS FFR catheter is used during the protocol and should equal 1.0.
 - b. Resting Pd/Pa and dPR
 - i. The RXi FFR microcatheter will be advanced 1-2cm just distal to the lesion of interest. Position microcatheter based on reference still images from diagnostic angiogram. Ensure the guide is cleared with saline if contrast is needed to position the catheter.
 - ii. An initial period of 20 seconds to provide stable assessment of resting physiology will be performed
 - iii. Resting gradient will be documented. dPR can be documented at same time (if available) or can be documented post-procedure after waveform analysis.

- c. Contrast Injection FFR (cFFR)
 - i. Injector-based intracoronary bolus of contrast with the ACIST automated injector will deliver contrast medium: Iopamidol (ISOVUE®-370), a low-osmolality contrast medium at 796 mOsmol/kg water
 - ii. Settings:
 - Rate of 4 mL/sec, volume of 10 cc (left coronary system)
 - Rate of 3 mL/sec, volume of 6 cc (right coronary system).
 - iii. Any deviation from these settings due to operator judgment will be documented.
 - iv. Inject contrast to fill guide catheter and wait for return of baseline hemodynamics.
 - v. Press record on ACIST FFR console and then inject contrast at standard settings above for cFFR. Within the first minute of contrast injection, the nadir cFFR value will be logged.
 - vi. The recorded tracings will be captured and saved for an independent FFR core lab review.
- d. Adenosine FFR (aFFR)
 - i. Return of baseline hemodynamics
 - ii. Intravenous adenosine administered at a rate of 140 µg/kg of body weight per minute x 2 minutes will then be performed and the aFFR value logged.
 - iii. If the aFFR is >0.80, then no PCI is performed and this final FFR value will be logged for correlation to long-term outcomes.
 - iv. If the aFFR is ≤0.80, then PCI according to standard techniques will be performed. Post-PCI, the NAVVUS FFR microcatheter will be used to measure resting Pd/Pa, dPR, contrast FFR, and adenosine FFR in the same manner as above with values recorded.
 - v. The recorded tracings will be captured and saved for an independent FFR core lab review.

5. Drift

- a. Drift check will be performed at least once during each procedure and ideally after each use/measurement of the NAVVUS FFR microcatheter
- b. Clinically significant drift will be defined as $> \pm 0.03$ (12).
- c. The presence of any significant drift (yes/no) will be recorded. If there is clinically significant drift, the FFR measurements will be repeated after repositioning of the guide catheter and re-equalization.

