9.3 Primary Endpoint Analysis

9.3.1 Quantitative Method Comparison Between Contrast Fractional Flow Reserves and Adenosine Fractional Flow Reserves

Contrast FFR and aFFR will be quantitatively compared using the procedure described in *CLSI EP09-A3 Measurement Procedure Comparison And Bias Estimate Using Patient Samples Approved Guideline* (18). A summary of this comparison is described below.

The measurements from the 2 methods will be plotted against each other. The aFFR will be plotted on the x-axis, and the cFFR will be plotted on the y-axis. The plot will be examined for highly influential points and heterogeneity of variance along the range of measurement values. In addition, several types of difference plots similar to the Bland-Altman plot will be used to examine whether:

- the size of the variance changes with changing measurement value
- the bias changes with changing measurement value
- the coefficient of variation changes with changing measurement value

Based on the above information, the appropriate model will be applied to describe the relationship of aFFR measured values to their corresponding cFFR values. Assuming:

- sample size of 208 pairs (see the next section) of FFR measurements
- linear model will be applied in quantitative method comparison
- width of the 2-sided 95% CI for the slope is expected to be ± 0.06
- width of the 2-sided 95% CI for the bias is expected to be within ± 0.06

9.3.2 Qualitative Method Comparison Between Contrast Fractional Flow Reserves and Adenosine Fractional Flow Reserves

The qualitative method comparison consists assessing the agreement as to which lesion is flow limiting. If a lesion has an adenosine FFR measurement \leq the cutoff value of 0.8, then the lesion is considered flow limiting. Using the model developed above, the contrast FFR measurement that corresponds to adenosine FFR measurement value of 0.8 will be used as the cutoff value for determining whether a lesion is flow limiting for contrast FFR. The expected cutoff value for the contrast FFR is 0.83.

The 2 methods will be compared qualitatively using the AUC under the ROC curve. The analysis will incorporate the following:

1. The contrast FFR will be the new diagnostic compared to the adenosine FFR as the reference standard.

2. The hypotheses will be designed to demonstrate that that AUC for these two methods is greater than 0.8.

The null and alternative hypotheses are as follows:

[figure not shown]
$$H_0: \text{ROC AUC} \leq 0.8$$

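### Left and right vessels get different contrast settings but share one cFFR cutoff, and no planned analysis checks whether that cutoff performs alike in both

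*Combined protocol and SAP*

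**What the plan says.** Protocol section 3.2.2, step 4c, sets two automated injections of the same agent: "Rate of 4 mL/sec, volume of 10 cc (left coronary system") and "Rate of 3 mL/sec, volume of 6 cc (right coronary system"). Operator deviations from them are documented. The reference method makes no such distinction: according to the synopsis, "adenosine for aFFR will be delivered systemically via intravenous infusion", and step 4d gives one weight-based rate for every vessel.

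Section 9.3.1 says that, after the plots have been inspected, "the appropriate model will be applied to describe the relationship of aFFR measured values to their corresponding cFFR values". For planning it assumes that a "linear model will be applied in quantitative method comparison". Section 9.3.2 reads the cutoff from that fit: "the contrast FFR measurement that corresponds to adenosine FFR measurement value of 0.8 will be used as the cutoff value". One value, 0.83, is expected, and one AUC is tested against 0.8.

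The diagnostics in 9.3.1 cover influential points and whether variance, bias and coefficient of variation change along the measurement range. Nowhere in section 9 is there a left/right term, stratum, interaction or by-system table.

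**The concern.** Section 1 names as a significant limitation of the 763-patient comparison its "lack of a standardized protocol for the type, volume, and rate of intracoronary contrast injection". It makes the hypothesis that standardizing these parameters may improve accuracy the basis of this trial, and section 3.3.1 defines the primary endpoint by a standardized volume and rate. Yet there are two standards, and the plan never asks whether cFFR tracks aFFR in the same way under each.

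An offset between systems is a difference between groups at the same measured value, so plots against measured value are not built to show it. A pooled cutoff would then lie between the two system-specific cutoffs: too low for the system with higher cFFR and too high for the other. A reader would receive one cutoff with one sensitivity and one specificity, and could not tell whether these describe either system.

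**Working it through.** **The plan's own figure.** The 208 pairs in 9.3.2 reproduce with the Obuchowski binormal variance, V = 0.0099·exp(−A²/2)·[(5A²+8) + (A²+8)/R], where A = 1.414·z(AUC) and R = 1.06.
- V(0.8) = 0.1169 and V(0.9) = 0.0672.
- Positives = [1.960·√0.1169 + 1.282·√0.0672]² / 0.1² = 100.5, rounded up to 101.
- Negatives = 1.06 × 101 = 107, total 208.

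The formula has no vessel input, so a supportive left/right analysis leaves it unchanged.

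**The settings.** The right bolus is 6/10 of the left volume (40% less) at 3/4 of the rate (25% slower). It lasts 6/3 = 2.0 s, against 10/4 = 2.5 s.

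**Assumed inputs (not in the documents).** aFFR mean 0.80 and SD 0.10; residual SD 0.04; slope 0.8; 30% right-system vessels; right-system offset d of 0 to 0.03. From the documents: the aFFR threshold 0.80 and the expected cFFR cutoff 0.83. The model is cFFR = 0.83 + 0.8·(aFFR − 0.80) + d·right + error. The implied correlation at d = 0 is 0.08/√(0.08² + 0.04²) = 0.89.

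**Pooled cutoff.** This is 0.83 + 0.3d, which is 0.3d above the left system's own cutoff and 0.7d below the right's. At d = 0.03 it is 0.839: 0.009 too high for left and 0.021 too low for right.

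**Simulated performance at the pooled cutoff (2,000,000 lesions per row).**

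| d | Right sens. | Right spec. | Right accuracy | Left sens. | Left spec. | Left accuracy | Pooled AUC |
|---|---|---|---|---|---|---|---|
| 0 | 0.85 | 0.85 | 0.853 | 0.85 | 0.85 | 0.852 | 0.936 |
| 0.01 | 0.82 | 0.88 | 0.851 | 0.87 | 0.84 | 0.852 | 0.935 |
| 0.02 | 0.78 | 0.91 | 0.844 | 0.88 | 0.82 | 0.851 | 0.933 |
| 0.03 | 0.74 | 0.93 | 0.836 | 0.89 | 0.81 | 0.849 | 0.930 |

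The AUC within each system stays at 0.936 in every row. With d = −0.03 the pattern reverses, and right-system specificity is 0.74.

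**Visibility in the planned plots.** The pooled residual SD at d = 0.03 is √(0.04² + 0.3·0.7·0.03²) = 0.0423, against 0.0400 with no offset.

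**Other assumptions.** With r = 0.94 (the correlation cited in section 1), aFFR mean 0.805, SD 0.09 and 30% right, d = 0.03 takes right sensitivity from 0.89 to 0.78 and pooled AUC from 0.963 to 0.957. Over offsets of 0.01-0.05, 20-40% right and r of 0.85-0.94, right sensitivity runs from 0.86 down to 0.64, and pooled AUC falls by at most about 0.02.

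**Precision of the check.** At the cap of 200 patients, one vessel each, with 60 right and 140 left, the 95% half-width for the offset is 1.96·0.04·√(1/60 + 1/140) = 0.012. With aFFR SD 0.09 and 20-40% right it is about 0.009-0.011 at r = 0.94 and 0.016-0.019 at r = 0.85.

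**The case against.** The strongest reply is that two fixed, automated, vessel-specific settings with one agent are a standardized protocol. The problem named in sections 1 and 5 is uncontrolled variation between operators, injection methods and agents. The two settings may have been chosen to give comparable hyperemia. That stands: the documents neither say nor imply that an offset exists, and section 1 offers the effect of volume and rate as a hypothesis, not a finding. But neither do they say that the settings are equivalent, and no planned analysis would show it.

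It is also true that the open wording on the model permits a vessel term, and that section 3.2.3 has procedural characteristics entered in the eCRF, so the question could be examined later. A term chosen after seeing the data would, however, be post hoc.

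A reader might infer that pooling undermines the primary test, because the pooled AUC mixes two tests and so describes neither setting. The working does not support this. A constant offset leaves each within-system AUC unchanged and slightly lowers the pooled one, so under this model a pooled AUC above 0.8 implies the same in both systems. A reader might also read the fall in right sensitivity as a plain loss. It is mainly a trade against specificity: overall accuracy falls by at most about 1.7 points in the right system and 0.3 in the left.

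**Conclusion.** The gap is real but conditional. Two contrast settings feed one model and one cutoff, and the planned diagnostics would not separate a left-right offset from scatter. Under the assumed offsets of 0.01 to 0.03 the pooled cutoff shifts the systems in opposite directions, and the less frequent one most: right sensitivity loses 3 to 11 points and right specificity gains 3 to 8. With no offset the two systems behave alike. The offset, vessel mix, slope and SDs are all assumptions.

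What is at stake is whether the published cutoff, sensitivity and specificity can be claimed for both settings. The AUC hypothesis test is not at risk. Nor is the treatment of enrolled patients, since section 3.2.2 bases the PCI decision on aFFR. This point takes no view on which contrast setting is right.

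**What to change.** Keep the pooled model, cutoff and AUC test as the primary analysis. In sections 9.3.1 and 9.3.2 prespecify one supportive analysis:
- add coronary system (left/right) and its interaction with aFFR to the model;
- report the left-right difference in cFFR at aFFR 0.80 with its 95% CI;
- report sensitivity and specificity at the pooled cutoff, and AUC, separately by system with 95% CIs;
- state that any claim that one cutoff serves both settings will be supported or qualified by these results.

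A rule that switches to separate cutoffs when the systems appear to differ is not recommended. It would need a criterion for a difference, and would let the number of cutoffs depend on roughly 60 right-system pairs.

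The cost is two model terms and one table, using the target vessel known for each patient, with no new data and no change to the 208 pairs. The drawback is precision. With about 30 positive lesions among 60 right-system vessels, a sensitivity of 0.78 has a half-width of 1.96·√(0.78·0.22/30) = 0.15. A test of AUC above 0.8 in the right system alone would have only about 20-45% power. The by-system results should therefore be labelled as estimates, not powered tests.
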